Secondary: 1) Correlate effects on neurophysiology test perimeters with known drug side effects. 2) Pinpoint where in neuroaxis perampanel exerts maximal effects, which may shed light on where it exerts its anti-seizure effects.

Based on similar studies, we will recruit 12 subjects. Each subject will undergo 4 neurophysiology tests. Then each subject will ingest perampanel and then repeat the 4 neurophysiology tests. We will compare the pre-ingestion to the post-ingestion values in the 4 tests using a Wilcoxon signed-rank test, which is more appropriate for small samples than a standard paired t-test. We do not expect any dropouts, but if they occur we will perform sensitivity analysis by providing results for different imputed values for the dropouts.

INCLUSION AND EXCLUSION CRITERIA

Healthy subjects between the ages of 18 to 50 years old with a body mass index of 19-29 kg/m² will be recruited. Subjects would be excluded if they use recreational drugs and have any neurologic disease, psychiatric condition or any other condition that may affect outcome and risk subject safety.

Furthermore, anyone that would not be able to participate in neurophysiology tests will also be excluded. Subject will also be excluded should they take any over the counter medication or consume caffeine or alcohol 12 hours prior to the study.

DATA AND SAFETY MONITORING PLAN

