The risk to subjects is minimal risk for all tests involved. Blood levels of perampanel will be drawn 1 hour after drug administration. Additionally, the 4 tests (VEP, EEG, SEP, BAEP) will be completed both prior to and following study drug administration. This study does not have interim and complete stopping rules. This is a small study and we do not expect to encounter any major adverse events since the tests we will be administering is well tolerated and the study drug, perampanel, is FDA approved and well tolerated in the way we will be administering it (single dose at 6mg). We do not expect any adverse events that would stop a subject's participation. The subject can withdraw voluntarily. The risk of taking perampanel to the subject is classified as greater than minimal risk. In a small study looking at single dose of perampanel administered to healthy volunteer at 6mg, the reported side effects were headache, dizziness (excluding vertigo), somnolence, and fatigue. These were all classified as mild to moderate in severity. Rate of side effect was reported as 16.8% while placebo was 12.6%. Serious Side Effects: Perampanel may cause new or worse aggressive behavior, homicidal thoughts or threats, hostility, anger, anxiety, irritability, being suspicious or distrustful (believing things that are not true), and other unusual or extreme changes in behavior or mood. You should contact the study doctor immediately should you experience any of the above. Antiepileptic drugs, including perampanel, may cause suicidal thoughts or actions in a very small number of people, about 1 in 500. Study subjectss should call their healthcare providers right away if they have any of the following symptoms, especially if they are new, worse, or worrisome: thoughts about suicide or dying, thoughts of self-harm, attempt to commit suicide, new or worse depression, new or worse anxiety, feeling agitated or restless, panic attacks, trouble sleeping (insomnia), new or worse irritability, acting aggressive, being angry or violent, acting on dangerous impulses, an extreme increase in activity and talking (mania), and other unusual changes in behavior or mood. You should call your study doctor immediately if you notice any changes in mood, ideas or behavior. Most common side effects: Dizziness, fatigue, sleepiness, irritability, falls, nausea, imbalance, gait problems, vertigo, and weight gain. Less commonly seen side effects: Headache, anxiety, upset stomach, vomiting, constipation, urinary tract infection, problems with coordination, rash, bruises, muscle pain, blurry vision, swelling of arms/legs, numbness, memory problems, confusion, euphoria, low blood sodium level, increase triglyceride level, skin laceration, pain in extremities, back pain, and head trauma. Additional Risks: The U.S Drug Enforcement Agency (DEA) may classify some, but not all, medicines as controlled substances. Perampanel has been classified as schedule III. Medicines in this category have an approved medical use but have potential for abuse, physical dependence, or psychological dependence. The risk is lower compared to drugs in Schedule I and II. Some other anti-epileptic medicines have also been listed as controlled substances. It is possible that perampanel may interact with other medicines and herbal supplements that you are taking. Before starting the study, your study doctor will determine that you are not taking anything that can interact with perampanel. During the collection of blood samples, you may experience slight discomfort and a small amount of bleeding, discoloration or bruising at the site where the needle was inserted. Clot formation and infections may occur at the puncture site, but this is extremely rare. Fainting may occur during or

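### The monitoring plan rules out stopping rules for a drug it classes as greater than minimal risk, and ties no event to holding the dosing of the next subject (low priority)

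*Protocol*

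**What the plan says.** All of this stands in the protocol, mostly under Data and Safety Monitoring Plan.

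- **Stopping rules.** "This study does not have interim and complete stopping rules". The reasons given are the small size of the study, the approved status of the drug, its tolerability as a single 6 mg dose, and that "we do not expect to encounter any major adverse events". Similar reasons are given for having no interim analysis and no data safety monitoring board.
- **Risk class.** The tests are called minimal risk. For the drug, "The risk of taking perampanel to the subject is classified as greater than minimal risk".
- **Serious effects listed.** "Perampanel may cause new or worse aggressive behavior, homicidal thoughts or threats, hostility, anger, anxiety, irritability", among others. Antiepileptic drugs, perampanel included, "may cause suicidal thoughts or actions in a very small number of people, about 1 in 500".
- **Evidence at this dose.** In a small study of a single 6 mg dose in healthy volunteers, all reported side effects were mild to moderate. The side-effect rate is given as 16.8%, against 12.6% on placebo.
- **Safeguards.** The exclusions under Inclusion and Exclusion Criteria cover "psychiatric condition or any other condition that may affect outcome and risk subject safety". An investigator stays with the subject, events are rated mild, moderate or severe and go to the IRB and the sponsor, and the principal investigator monitors safety. For effects noticed later, "You should call your study doctor immediately if you notice any changes in mood, ideas or behavior".
- **Design.** Twelve healthy men each take one dose, and participation ends after the post-dose tests (Study Design). No dosing order or spacing is given.

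**The concern.** The plan settles the stopping question in the negative, so this is not a detail left to a statistical analysis plan. Its main argument is that no major event is expected. That bears on how often a rule would be needed, but not on what to do if an event occurs.

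The gap is narrow. Severity is recorded but linked to no action. The section mentions study closure and termination of a subject, yet gives no criterion for either and names nobody to decide. Voluntary withdrawal protects only the subject who withdraws. If one volunteer had a serious psychiatric reaction, nothing in the protocol would require the site to wait before dosing the next.

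At stake is the safety of healthy volunteers, with no therapeutic need for the drug, who are still undosed when such an event occurs. The pre/post comparison, its error rate and the conclusions on the neurophysiology tests are not affected.

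**Working it through.** The protocol gives no figure to reproduce here. The check asks how often a one-event hold would fire and how much it could prevent.

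**Inputs**
- n = 12 subjects, one dose each (Study Design).
- p = 1/500 = 0.002 for suicidal thoughts or actions (Data and Safety Monitoring Plan). This is a general antiepileptic figure, not tied to a single dose.
- p = 0.01 to 0.05 for all serious or severe related events. This is **assumed**, because the protocol gives no such rate.
- Events are taken as independent between subjects with constant p.
- Dosing is either one at a time or in groups of three. Both are assumptions.

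**Formulas**
- Chance that the hold fires: F = 1 − (1−p)^12.
- Expected number dosed if dosing stops at the first event: D₁ = F/p one at a time; D₃ = 3F / [1 − (1−p)³] in groups of three.
- Mean number still undosed when the hold fires: (12 − D)/F.
- Expected events avoided per study: p(12 − D).

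**Worked case, p = 0.01**
- F = 1 − 0.99^12 = 0.1136.
- D₁ = 0.1136/0.01 = 11.36. Undosed: 0.638/0.1136 = 5.62. Avoided: 0.01 × 0.638 = 0.0064.
- D₃ = 3 × 0.1136/0.0297 = 11.48. Undosed: 0.524/0.1136 = 4.61. Avoided: 0.01 × 0.524 = 0.0052.

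**Results**

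| p | Hold fires | Undosed when it fires: singly / threes | Events avoided: singly / threes |
|---|---|---|---|
| 0.002 (documented) | 2.4% | 5.5 / 4.5 | 0.00026 / 0.00021 |
| 0.01 (assumed) | 11.4% | 5.6 / 4.6 | 0.0064 / 0.0052 |
| 0.05 (assumed) | 46.0% | 6.1 / 5.1 | 0.140 / 0.117 |

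The events-avoided figures are upper bounds. They suppose that dosing stops for good after the first event and that every event is known before the next dosing.

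**Choice of trigger.** If 16.8% is the share of subjects with any side effect (an assumption, since the protocol does not say what it is a rate of), a hold on any adverse event would fire with probability 1 − (1 − 0.168)^12 = 89.0%. The trigger therefore has to be limited to serious or severe, possibly related events.

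**How far the earlier evidence reaches.** Background mentions a study of 6 patients at 6 mg. If that is the small study cited in the monitoring plan (an assumption), no severe event in 6 leaves a one-sided 95% upper limit of 1 − 0.05^(1/6) = 39%. It is reassuring, but it cannot exclude uncommon severe events.

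**The case against.** The strongest reply is that this is a reasoned choice and not a mistake. The protocol says openly that it has no rule and explains why. The only severity evidence it cites at this dose, in healthy volunteers, is mild to moderate throughout, while the proposed trigger is serious or severe events. At the one documented rate the benefit is about 0.0003 events per study, and every larger figure comes from an assumed rate. The bounds would shrink further in practice: the principal investigator may resume dosing, and events after the session come to light only if the subject makes contact. For suicidal symptoms the section first directs subjects to their healthcare providers. The principal investigator already monitors safety and would probably pause anyway, and nothing suggests that subjects would be dosed together.

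Most of this stands, and it sets the priority low. It does not remove the gap, because none of the safeguards says what happens to the next subject, and a hold is meant for the case where expectations prove wrong.

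A reader might infer more than the documents support:

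- **That the section contradicts itself on risk.** It does not. Minimal risk refers to the tests and greater than minimal risk to the drug, and nothing in the protocol says that the latter class requires a stopping rule.
- **That subjects are unprotected.** They are not. Exclusions, constant attendance, grading, reporting and a contact instruction are all in place.
- **That a monitoring board, an interim analysis or a statistical boundary is needed.** Nothing here calls for one in 12 subjects given a single dose.

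**Conclusion.** The point holds as a low-priority safety improvement. The protocol rules out stopping rules and leaves no event tied to holding the next subject's dosing, although it recognises serious psychiatric risks of the drug. It is not an analysis error.

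The expected benefit is very small if the documented rate is the relevant one, and modest even at an assumed 5%. The case for the change is that it costs little, and that if a serious event did occur about half the cohort (roughly 5 to 6 of 12) would on average still be undosed. This rests on independent events, a constant rate, dosing singly or in groups of three, and, above the documented 1 in 500, an assumed rate.

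**What to change.** Replace the sentence on stopping rules in the Data and Safety Monitoring Plan with:

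> There is no statistical stopping rule. Subjects are dosed one after another or in groups of at most three. If a serious adverse event (including suicidal or homicidal thoughts or behaviour), or any adverse event rated severe, is judged possibly related to perampanel, whether seen in the session or reported later, no further subject is dosed until the principal investigator has reviewed it, reported it to the IRB and the sponsor, and recorded the decision to resume or stop.

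The protocol defines neither seriousness nor relatedness. Add one line defining serious (death, threat to life, hospital admission, lasting disability, and the psychiatric events above) and have the principal investigator judge relatedness. The rest uses the existing severity grades, reporting lines and contact instruction. No follow-up visit is added.

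The cost is one short paragraph, a cap on how many subjects are dosed together, and a recruitment pause when the hold fires. The sample size and the analysis do not change.
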